16.2. Study records retention

Study documents should be retained for a minimum of 2 years after the investigation is discontinued and FDA notified. No records will be destroyed without the written consent of the sponsor, if applicable. It is the responsibility of the sponsor to inform the investigator when these documents no longer need to be retained.

16.3. Protocol deviations

A protocol deviation is any noncompliance with the clinical trial protocol or GCP requirements. The noncompliance may be either on the part of the participant, the investigator, or the study site staff. As a result of deviations, corrective actions are to be developed by the site and implemented promptly.

It is the responsibility of the site to use continuous vigilance to identify and report deviations within 5 working days of identification of the protocol deviation, or within 5 working days of the scheduled protocol-required activity. All deviations must be addressed in study source documents and reported in

the ADCS EDC system. Protocol deviations must be sent to the IRB of record, per IRB reporting guidelines.

16.4. Publication and data sharing

The International Committee of Medical Journal Editors (ICMJE) member journals have adopted a clinical trials registration policy as a condition for publication. The ICMJE defines a clinical trial as any research project that prospectively assigns human subjects to intervention or concurrent comparison or control groups to study the cause-and-effect relationship between a medical intervention and a health outcome. Medical interventions include drugs, surgical procedures, devices, behavioral treatments, process-of-care changes, and the like. Health outcomes include any biomedical or health-related measures obtained in patients or participants, including pharmacokinetic measures and adverse events. The ICMJE policy, and the Section 801 of the Food and Drug Administration Amendments Act of 2007, requires that all clinical trials be registered in a public trials registry such as ClinicalTrials.gov, which is sponsored by the National Library of Medicine. This trial will be registered through ClinicalTrials.gov (NCT03061474).

At a minimum, electronic item-level data from this trial will be made publicly available through the ADCS Data Sharing Process, one year after publication of the primary outcome results, in accord with the data-sharing policy of this NIH-funded trial organization.

APPENDIX 1.

Table 1. Study schedule of events.										
Week	*	*	*	0	2	4	12	24	36	48 (or early termination)
Visit	SC v1	SC v2	SC v3	V1	@	@	V2	V3	@	V4^
ICF/HIPAA	X									
Demographics/medical history	X									
Concomitant medications	X			X	X	X	X	X	X	X
Adverse events	X			X	X	X	X	X	X	X
Physical/neurological exams	X			X			X	X		X
Vital signs	X			X			X	X		X
MMSE	X			X				X		X
CDR-SB	X							X		X
Wechsler Logical Memory II	X									
Free and cued selective reminding task (FCSRT)	X									
Assessment of inclusion/exclusion criteria	X									
Blood draw (safety laboratories)	X			X				X		X
Fasting blood draw (future biomarkers)		X					X	X		X
Blood draw (drug levels)							X	X		X
Urinalysis	X			X				X		X
Electrocardiogram (EKG)	X							X		X
Blood draw (APOE genotyping)	X									
GDS	X			X				X		X
Lumbar puncture		X [#]								X
MRI			X							X
ADAS-cog				X				X		X
ADCS-ADL-MCI				X				X		X
C-SSRS				X				X		X
Dispense study drug				X			X	X		X ^π
Distribute study medication diaries				X			X	X		
Collect completed study medication diaries							X	X		X
Assess treatment assignment blindness										X

* 60 days are allotted to complete the screening assessments

[#] Must be performed within 30 days of platelet level and coagulation parameters (SC v1 blood panel). In the event of inability to procure adequate sample, may be performed under guided fluoroscopy, which may require additional visits.

@ Telephone visits will assess safety and adverse events

^ In the event of early termination due to participant withdrawal of consent or removal by investigator, the end of study visit should be completed.

^π Participants will be administered blinded study drug at the end of study visit as part of an extension study, until the go/no-go analyses are complete. If a go decision is achieved, participants will be enrolled in an extension study.

MMRM	Mixed model for repeated measures
MMSE	Mini Mental State Exam
PID	Participant Identification Number
PK	Pharmacokinetic
PP	Per protocol set
PT	Preferred term
QD	Quaque die (once daily)
SAE	Serious adverse event
SAP	Statistical analysis plan
SD	Standard deviation
SOC	System organ class
ULN	Upper limit of normal
WHO Drug	World Health Organization drug reference dictionary

1 INTRODUCTION

1.1 Introduction

This document presents the statistical analysis plan (SAP) for the protocol titled: A Phase 2, Proof-of-Concept, Double-Blind-Randomized, Placebo-Controlled Adaptive Design Trial of Nicotinamide in MCI due to AD and Mild AD Dementia (NEAT). This study is a multisite, randomized, double-blind, placebo-controlled Phase 2 trial comparing efficacy and safety of nicotinamide versus placebo in patients with MCI due to AD and Mild AD Dementia.

This SAP is based on Version 4.0, Amendment 3, of the NEAT Protocol dated 28Dec2017. It contains the analysis details and methodology to answer the study objectives, including planned summary tables, by-subject listings, and figures, which will provide the basis for the results section of the clinical study report (CSR). Operational aspects related to collection and timing of planned clinical assessments are not repeated in this SAP unless relevant to the planned analyses.

1.2 Randomization Methodology

The ADCS Safety Biostatistics group oversaw the randomization scheme, which was administered through the EDC. Randomization incorporated blocking to maintain temporal balance between arms and was stratified to ensure balance across likely correlates of the study outcome. Specifically, randomization was stratified by site, diagnostic category (MCI or dementia), and APOE genotype ($\epsilon 4$ carriers, $\epsilon 4$ non-carriers).

1.3 Power and Sample Size Determination

Based upon prior reported data, it is expected that the change in p-tau₂₃₁ over one year will be approximately 5.1 pg/ml with a standard deviation of 1.5. With a sample size of 48 participants, a 1:1 randomization scheme, and a 10% per year loss-to-follow-up rate, the proposed study will attain approximately 80% power for detecting a true absolute difference in mean within-subject change in p-tau₂₃₁ of 1.26 pg/ml (24.5% relative reduction).

2 OBJECTIVES AND OUTCOMES OF STATISTICAL ANALYSIS

2.1 Primary Objectives and Outcomes

- **Primary Objective 1:** Determine if daily treatment with high dose nicotinamide reduces levels of phosphorylated tau (p-tau₂₃₁) over 48 weeks in individuals with MCI due to AD and mild probable AD dementia
- **Primary Objective 2:** Assess the safety and tolerability of high-dose nicotinamide treatment in individuals with MCI due to AD and mild probable AD dementia, as assessed by:
 - Vital signs,

- Treatment emergent adverse events,
- Serious adverse events
- Suicidality rating scale scores,
- ECG abnormalities.

2.2 Secondary Objectives and Outcomes

- **Secondary Objective 1:** Determine if daily treatment with high-dose nicotinamide in individuals with MCI due to AD and mild AD dementia can affect CSF levels of:
 - amyloid beta (A β 42)
 - amyloid beta (A β 40)
 - phosphorylated tau (p-tau₁₈₁)
 - total tau (t-tau)
 - the ratio of total tau/A β 40
 - the ratio of total tau/ A β 42
- **Secondary Objective 2:** Determine if daily treatment with high-dose nicotinamide in individuals with MCI due to AD and mild AD dementia reduces the rate of cognitive decline, as assessed by:
 - ADAS-Cog 13
- **Secondary Objective 3:** Determine if daily treatment with high dose nicotinamide in individuals with mild AD dementia or MCI due to AD reduces the rate of functional decline and everyday activities as assessed by:
 - ADCS-ADL-MCI
 - CDR-SB

2.3 Exploratory Objectives and Outcomes

- **Exploratory Objective 1:** Determine if daily treatment with high-dose nicotinamide reduces rate of brain volumetric changes atrophy in individuals with MCI due to AD and mild AD dementia, as assessed by:
 - whole brain volume,
 - ventricular volume,
 - hippocampal volume,
 - and cortical thickness
- **Exploratory Objective 2:** Determine the effect size of daily treatment with high dose nicotinamide over 48 weeks in individuals with mild AD dementia or MCI due to AD on:
 - phosphorylated tau (p-tau₁₈₁)
- **Exploratory Objective 3:** Estimate the association between blood levels of nicotinamide and change in CSF p-tau₂₃₁.

- **Exploratory Objective 4:** Describe efficacy data by the randomization factors of diagnostic category (MCI or dementia), and APOE genotype ($\epsilon 4$ carriers, $\epsilon 4$ non-carriers)

3 STUDY DESIGN

3.1 Synopsis of Study Design

Forty-seven participants were randomized to 1500 mg BID nicotinamide or matched placebo at a 1:1 ratio, stratified by site, diagnostic category (MCI or dementia), and APOE genotype ($\epsilon 4$ carriers, $\epsilon 4$ non-carriers).

There was a screening period of up to 60 days, during which each participant completed 3 screening visits.

The ADAS-Cog 13, ADCS-ADL-MCI and CDR-SB were collected at 3 timepoints: baseline, week 24, and week 48. The MMSE was collected at screening visit 1, baseline, week 24, and week 48. the Free and Cued Selective Reminding Task (FCSRT) was only done at screening visit 1.

Lumbar punctures and MRI scans were performed at screening and week 48. Safety measures including the C-SSRS, EKG, and safety laboratories were collected at screening or baseline, week 24, and week 48. Vital signs, blood collection for biomarker banking, physical exams, and neurological exams were done at screening or baseline, week 24, week 36, and week 48. Concomitant medications and adverse events were collected at every visit.

4 PARTICIPANT POPULATIONS

4.1 Population Definitions

The following populations will be evaluated and used for presentation and analysis of the data:

- **Enrolled Participants:** Participants who signed an informed consent form and were assigned a Participant Identification number (PID)
- **Intent to Treat (ITT) Population:** All enrolled participants who received a randomized treatment assignment.
- **Safety Population:** Enrolled and randomized participants who received at least 1 dose of blinded study therapy (nicotinamide or placebo). This will be the primary analysis population used for the safety analyses.
- **Modified Intent-to-Treat (mITT) population:** All randomized participants who have a baseline assessment of the endpoint, and who have at least one evaluation of the endpoint following baseline.

- **Per-protocol population:** All randomized participants who completed trial activity through week 48 including lumbar puncture.

5 STATISTICAL METHODS

5.1 Primary Efficacy Analysis

The primary outcome measure of phase 2a is the within-participant change in p-tau₂₃₁ from baseline to week 48. The primary analysis will be conducted on the ITT population. No missing data will be imputed

The change in p-tau₂₃₁ will be modeled using an analysis of covariance model (ANCOVA). That is, 48-week p-tau₂₃₁ will be regressed upon baseline p-tau₂₃₁ and an indicator for treatment vs. placebo using a linear regression model of the form:

$$E[ptau_{231,post}] = \beta_0 + \beta_1 I_{Nic} + \beta_2 ptau_{231,pre}.$$

β_1 represents the parameter of interest. The Huber-White robust variance estimator¹ will be used to estimate the variance of the estimated difference in the mean change in p-tau₂₃₁ comparing treatment to placebo. Specifically, the variance estimator for the estimated treatment effect will be the (2,2) element of

$$(X^T X)^{-1} X^T \hat{\Sigma} X (X^T X)^{-1},$$

where X denotes the $n \times 3$ design matrix from regression model, $\hat{\Sigma}$ is the $n \times n$ diagonal matrix with the squared model residuals on the diagonal and 0 on the off-diagonal, and n the number of observations included in the analysis. Along with the estimated difference in mean change in p-tau₂₃₁, a Wald-based 95% confidence interval and corresponding p-value will be computed and presented.

Sensitivity analyses for the primary outcome

An exploratory sensitivity analysis will investigate compare within-patient change in pTau₂₃₁ in the per-protocol population. Sensitivity analyses for the impact of potential missing data will be conducted for the primary outcome as described in Section 5.8.

5.2 Analysis of Safety Outcomes

Safety analyses will be conducted on the Safety Population.

The safety and tolerability of high-dose nicotinamide treatment in individuals with MCI due to AD or mild AD dementia will be assessed by the following, for each arm separately:

- Treatment emergent Adverse Events (TEAEs) summarized:
 - Overall and by number of subjects with an AE
 - By severity and relation to investigational product

- By number of events and by subjects with an event by System Organ Class (SOC)
- By Preferred Term (PT) within SOC
- Serious adverse events (SAEs) including deaths summarized as for TEAEs
- Vital signs (weight, BMI, blood pressure, pulse) will be presented with means and standard errors at each study visit
- Descriptive statistics for ECG interval data will also be reported across visits including baseline, week 24 and week 48 or early termination.
 - Proportion of subjects with at least 1 abnormal ECG by treatment arm
 - Proportion of subjects with at least 1 abnormal QTC by treatment arm
 - The QTC will be computed using the Friderica formula. Abnormal will be defined as above 460 for men and above 470 for women.
 - Average within subject change in QTC by treatment arm (baseline to latest available)
- Adverse events (AEs) leading to discontinuation

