9.2. Study Procedures

9.2.1. Visit schedule (see Appendix 1).

- Screening period: Three visits will determine eligibility. An initial clinical visit will include completion of informed consent, MMSE, Wechsler Logical Memory II, FCSRT, CDR-SB, GDS, physical and neurological examinations including vital signs, medical history and collection of concomitant medications, and assessment of inclusion and exclusion criteria. This visit will also include a blood draw for apolipoprotein E (APOE) genotyping, safety labs, urinalysis (UA), and electrocardiogram (EKG). Assuming that participants have had clinical neuroimaging within the previous 12-months to exclude the possibility of space-occupying lesion, the second visit will include lumbar puncture (LP) and fasting blood draw for future biomarker research. A third visit will include MRI for screening and baseline volumetric assessment. For participants lacking clinical neuroimaging in the previous 12-months, the order of LP and MRI visits may be reversed. If needed, redraw of blood can be performed to check platelet level and coagulation parameters within 30 days prior to LP.

- Active period: Eligible participants will have a brief physical and neurological exam including vital signs, collection of adverse events and concomitant medications, cognitive testing (MMSE and ADAS-cog), be administered the C-SSRS, GDS, and ADCS-ADL-MCI, will receive study medication, and undergo safety labs (blood and urine) at the baseline exam. Telephone follow-up at 2, 4, and 36-weeks will assess safety. At 12-weeks, an in-person visit will include a brief physical and neurological exam including vital signs, collection of adverse events and concomitant medications, blood collection for drug levels, fasting blood collection for future biomarkers, EKG, assessment of treatment compliance and administration of study medication. At 24 and 48-weeks, participants will undergo blood safety labs, urinalysis (UA), blood collection for drug levels, blood collection for future biomarkers, and EKG. Participants will complete the MMSE, ADAS-cog13, ADCS-ADL-MCI, CDR-SB, GDS, C-SSRS physical and neurological examinations, including vital signs, collection of adverse events and concomitant medications. MRI, LP, and fasting blood collection for future biomarkers will be performed at 48-weeks.

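### Vital signs, a named Primary Objective 2 measure, get visit-by-visit arm summaries but no within-participant change or baseline-adjusted difference, which costs precision for weight and BMI (minor, cheap to fix)

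*SAP*

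**What the plan says.** SAP 2.1 sets Primary Objective 2 as "Assess the safety and tolerability of high-dose nicotinamide treatment in individuals with MCI due to AD and mild probable AD dementia, as assessed by" a list of measures, and vital signs come first in it. SAP 5.2 says that safety "will be assessed by the following, for each arm separately", and for this item specifies: "Vital signs (weight, BMI, blood pressure, pulse) will be presented with means and standard errors at each study visit".

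The other places that could bear on vital signs are these:

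- **SAP 5.2, QTc item:** "Average within subject change in QTC by treatment arm (baseline to latest available". It names no SD or interval. It is relevant only because it shows that change was planned for another safety measure in the same list.
- **SAP 5.9:** gives default descriptives for continuous variables (N, mean, SD, quartiles, range) and defines change from baseline, but does not say which variables will have change tabulated.
- **SAP 5.6:** tabulates vital signs at baseline only.
- **Protocol 14.6.1 and 14.6.2:** cover AE and SAE summaries and comparisons, and descriptive displays of safety outcomes by subgroup.

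None of these assigns paired change, or an arm difference adjusted for baseline, to vital signs.

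**The concern.** Weight and BMI differ widely between people but usually move little within a person over a year. The SE of an arm mean at one visit therefore reflects mostly between-person spread. A reader can subtract the baseline mean from the week-48 mean to get a rough mean change. The reader cannot attach a valid SE to it, because that SE needs the baseline-to-follow-up correlation, which visit summaries do not contain.

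Dropout adds a second difficulty: the baseline and week-48 means then describe different sets of people, so part of the apparent change is a change of membership.

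At stake is how clearly a drug-related shift in weight or BMI could be seen, or ruled out, for a measure listed under a primary objective. The data for a sharper summary are collected anyway.

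**Working it through.** **Sample size.** The documents give no figure for vital signs. The only stated figure that uses the per-arm n is the primary power in SAP 1.3: 48 randomised, 10% loss, difference 1.26, SD 1.5. With 48 × 0.9 / 2 = 21.6 per arm, SE = 1.5 × sqrt(2/21.6) = 0.456. Then 1.26/0.456 − 1.96 = 0.80, giving power of 78.8% against the stated figure of about 80%. It reproduces. SAP 3.1 reports 47 randomised, so n at week 48 is 47 × 0.9 / 2 = 21.15 per arm, or 23.5 with no loss.

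**Assumptions.** The documents give no SD or correlation r for any vital sign. Assumed here: weight SD 15 kg (range 12–18), BMI SD 4–6 kg/m², r = 0.95 (range 0.90–0.97) for both, and r = 0.4–0.7 for blood pressure.

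**Formulas for the SE of a week-48 arm difference**

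- Raw means: SD × sqrt(2/n)
- Change scores: SD × sqrt(2(1 − r)) × sqrt(2/n)
- Baseline-adjusted: SD × sqrt(1 − r²) × sqrt(2/n)

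The adjusted-to-raw ratio is sqrt(1 − r²), which depends on neither SD nor n. It is 0.436 at r = 0.90, 0.312 at 0.95 and 0.243 at 0.97. Raw uncertainty is therefore 2.3, 3.2 and 4.1 times the adjusted.

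**Weight, central case (SD 15, r 0.95, n 21.15)**

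- Raw SE 15 × 0.3075 = 4.61; half-width 1.96 × 4.61 = 9.0 kg
- Adjusted SE 4.61 × 0.312 = 1.44; half-width 2.8 kg
- No loss: 8.6 against 2.7 kg. With t quantiles (df about 40): 9.3 against 2.9 kg

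**95% half-widths over the assumed ranges**

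| Measure | Raw | Adjusted |
|---|---|---|
| Weight (kg) | 7.2–10.9 | 1.8–4.7 |
| BMI (kg/m²) | 2.4–3.6 | 0.6–1.6 |

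**What the added analysis could show.** If each contrast were tested, the difference with 80% power is 2.80 × SE: 12.9 kg raw (10.3–15.5) against 4.0 kg adjusted (2.5–6.8). Power for a true 2 kg difference is 7% raw (7–8%) against 28% adjusted (13–61%).

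**Blood pressure.** At r = 0.4 to 0.7 the adjusted SE is 0.92 to 0.71 of raw, and the change-score SE is 1.10 to 0.77 of raw. At the low end change scores are worse than raw means. Pulse is not quantified.

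**Membership effect of dropout.** With SD 15, random loss from 23.5 to 21.15 per arm moves an arm's mean weight with an SE of sqrt(225 × (1/21.15 − 1/23.5)) = 1.0 kg, with no change in anyone.

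**Which interval to use.** SAP 5.1 specifies the uncorrected Huber-White variance with Wald limits. In a simulation of that estimator (normal data, r = 0.95, 1.96 cut-off, 40,000 runs), a null interval excluded zero in 6.9% of runs at 21 per arm and 6.5% at 24/23. Ordinary least squares with t quantiles gives 5%. For two independent intervals, the chance that at least one excludes zero is 1 − 0.95² = 9.8% with least squares and t, and 1 − 0.931² = 13% with the SAP 5.1 variance.

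**The case against.** The strongest reply is that the SAP plans no arm contrast for vital signs, so the 9.0 kg half-width belongs to a comparison the plan never proposes. That is right. A reader might infer that the planned table itself reports a weight difference with a 9 kg margin. It does not: SAP 5.2 summarises each arm separately. The 9.0 kg is what someone who compares the week-48 means would face.

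Other points on that side:

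- **The display is more than means and SEs.** A reader might infer that nothing else is tabulated. SAP 5.9 adds default descriptives and SAP 5.6 adds baseline vital signs. What remains missing is the paired summary.
- **No hazard is documented.** A reader might infer that a weight effect is being hidden. The documents do not support this: Protocol sections 7 and 11.2 report no adverse event differences in the two large trials, and the problems described at higher doses are gastrointestinal symptoms, headache, lightheadedness and liver abnormalities. Weight and BMI are singled out because the precision gain is largest there.
- **Other routes exist.** Clinically noted cases still appear as TEAEs, and no test or decision rule uses these tables. This stands, but TEAEs do not show a mean shift. SAP 1.1 does not say which variables the by-subject listings cover, and Protocol 16.4 releases item-level data a year after the primary publication.
- **The visit weeks conflict, but that is a separate matter.** SAP 3.1 reports "Vital signs, blood collection for biomarker banking, physical exams, and neurological exams were done at screening or baseline, week 24, week 36" and week 48, whereas Protocol 9.2.1 says "At 12-weeks, an in-person visit will include a brief physical and neurological exam including vital signs" and "Telephone follow-up at 2, 4, and 36-weeks will assess safety"; Appendix 1 agrees with the protocol text. This is a documentation check. It has no bearing on precision and adds no weight here.

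**Conclusion.** The point holds as a minor improvement in reporting. For weight and BMI, the planned summaries leave out the paired information needed to judge change. An arm comparison made from week-48 means would carry about 2.3 to 4.1 times the uncertainty of a baseline-adjusted one. That ratio rests only on the assumed correlation of 0.90 to 0.97; the kilogram and BMI figures also rest on assumed SDs. In direction, baseline adjustment gains for any nonzero correlation, apart from the one degree of freedom spent, and change scores gain only above 0.5.

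The limits are plain. Weight and BMI are nearly one measure, the gain for blood pressure is modest, and a 2 kg difference would often stay unclear even with the added analysis. Nothing here affects the primary efficacy analysis or the go/no-go decision.

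**What to change.** In SAP 5.2:

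1. Keep the per-visit means and SEs.
2. At each post-baseline visit where vital signs were actually collected, add paired n, mean and SD of change from baseline by arm.
3. For weight and BMI only, add a week-48 arm difference from a regression of the week-48 value on baseline value and arm, with a 95% CI. Use ordinary least squares with t quantiles, or a small-sample-corrected robust variance such as HC3. Do not carry over the uncorrected variance and Wald limits of SAP 5.1. Label it descriptive and give no p-value.

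Settling week 12 against week 36 tells the programmer which columns to produce, but can be handled as its own correction.

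The cost is a few lines of SAP text and a few table columns, with no new data. The downside is two unadjusted descriptive intervals. With least squares and t quantiles, the chance that at least one excludes zero under no effect is at most 9.8%, and nearer 5% because BMI is weight rescaled by an almost fixed height. Restricting intervals to these two measures keeps that chance low.

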10.1.1. Inclusion Criteria

1. Age 50 or older
2. MCI or dementia due to AD
 - MCI due to AD²⁸:
 - Subjective memory complaint by the participant or an informant

- Memory impairment demonstrated by at least one of the following:
 - CDR memory box ≥ 0.5
 - Wechsler Logical Memory II ≥ 1.5 standard deviations below education adjusted mean
 - Less than or equal to 11 for 16 or more years of education
 - Less than or equal to 9 for 8-15 years of education
 - Less than or equal to 6 for 0-7 years of education
 - Free and Cued Selective Reminding Test (FCSRT) Total Recall score ≤ 39
 - FCSRT Free Recall score ≤ 24
 - FCSRT Delayed Free Recall score ≤ 8
 - Preserved functional independence/not demented, based on investigator clinical assessment
 - Probable AD dementia³⁰:
 - Cognitive impairment to a minimum of two domains that interferes with ability to function at work or at usual activities and represents a decline from previous levels
 - Insidious onset with gradual progression
 - Amnestic presentation or nonamnestic presentation (language, visuospatial, or executive dysfunction)
 - The presentation is not indicative of non-AD pathology (e.g., history of stroke or core features of Lewy body dementia, behavioral variant frontotemporal dementia, or non-AD primary progressive aphasia)
3. Biomarker criteria:
 - CSF $A\beta_{42} \leq 600$ pg/mL, or
 - A ratio of total tau to $A\beta_{42} \geq 0.39$
 4. Mini-Mental State Exam (MMSE) ≥ 20
 5. Blood laboratories (LFTs, CBC, etc), UA, and EKG are WNL or deemed clinically not significant by the site investigator
 6. Stable medications (including approved AD therapies) for at least 4 weeks prior to baseline
 7. At least 6 years of education
 8. Able to swallow oral tablets
 9. Speaks English fluently
 10. Available qualified study partner (≥ 3 times per week in-person communication with the participant)

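### SAP 5.2 does not limit the abnormal-ECG and abnormal-QTc proportions to post-baseline tracings, so an abnormality seen only before dosing can be counted as an event.

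*SAP*

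**What the plan says.** SAP 2.1 names ECG abnormalities among the measures of Primary Objective 2 (safety and tolerability). SAP 5.2 introduces the ECG summaries with "Descriptive statistics for ECG interval data will also be reported across visits including baseline, week 24 and week 48 or early termination". Nested under that line are "Proportion of subjects with at least 1 abnormal ECG by treatment arm" and "Proportion of subjects with at least 1 abnormal QTC by treatment arm". For QTc an absolute limit is given: "Abnormal will be defined as above 460 for men and above 470 for women". No definition is given for an abnormal ECG. The last item in the list is the mean within-subject QTc change by arm, from baseline to the latest available value.

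Protocol 10.1.1, criterion 5, admits participants whose "EKG are WNL or deemed clinically not significant by the site investigator". Protocol Appendix 1 shows an EKG at the first screening visit and none at week 0. SAP 5.9 defines baseline as the last assessment on or before the first day of study medication, so the screening tracing normally serves as the baseline tracing.

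Two other safety outcomes in the SAP are tied to treatment. Adverse events are summarised as treatment-emergent (5.2), and suicidality counts only positive answers given while on treatment (5.2.1).

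**The concern.** A safety proportion should describe what happened on treatment. A count of participants with at least one abnormal tracing is naturally pooled over visits. If the pre-dose tracing is in the pool, an abnormality that the drug cannot have caused counts the same as one that appeared at week 24. The QTc limit does not prevent this, because it is an absolute cut-off with no condition on change from baseline.

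The mean QTc change does use baseline as its reference, but it does not replace a count of new abnormalities. It is an average, so it can hide a few large individual shifts. It takes only the latest value, so a week-24 prolongation that has resolved by week 48 drops out. It also says nothing about abnormalities other than QTc.

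What is at stake is how readable one descriptive safety measure is. No efficacy inference depends on it, and the SAP plans no test of these proportions.

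**Working it through.** The documents state no rate or power for the ECG proportions, so there is no figure of the plan's own to reproduce.

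**Inputs**
- From the documents: 47 randomized 1:1 (SAP 3.1), about 23.5 per arm. The SAP schedule has one pre-dose tracing and two on-treatment tracings, at weeks 24 and 48 (SAP 3.1).
- Assumed, because the documents give none: b, the share abnormal before dosing, over 0 to 30%; and p, the new-abnormality rate among participants normal at baseline, 15% on nicotinamide and 5% on placebo.

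**Step 1. Counted rate with baseline included.** Everyone abnormal at baseline is an event; the rest become events at rate p:

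q = b + (1 − b)p

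With b equal in both arms, the expected difference is (1 − b)(p_T − p_C).

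| b | Nicotinamide | Placebo | Difference (points) | Ratio |
|---|---|---|---|---|
| 0 | 15.0% | 5.0% | 10 | 3.0 |
| 10% | 0.10 + 0.90 × 0.15 = 23.5% | 0.10 + 0.90 × 0.05 = 14.5% | 9 | 1.6 |
| 20% | 0.20 + 0.80 × 0.15 = 32.0% | 0.20 + 0.80 × 0.05 = 24.0% | 8 | 1.3 |
| 30% | 0.30 + 0.70 × 0.15 = 40.5% | 0.30 + 0.70 × 0.05 = 33.5% | 7 | 1.2 |

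**Step 2. The same in participants, at b = 20%.**
- Baseline included: 23.5 × 0.32 = 7.5 and 23.5 × 0.24 = 5.6, an excess of about 1.9.
- New abnormalities among the baseline-normal (23.5 × 0.80 = 18.8 per arm): 18.8 × 0.15 = 2.8 and 18.8 × 0.05 = 0.9, again an excess of about 1.9.

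The excess is the same; the baseline-inclusive count adds 23.5 × 0.20 = 4.7 expected background participants to each arm.

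**Step 3. Chance imbalance at baseline.** The standard deviation of the between-arm difference in baseline abnormality is √[b(1 − b)(1/23 + 1/24)]:
- b = 10%: 8.8 points
- b = 20%: √(0.16 × 0.0851) = 11.7 points
- b = 30%: 13.4 points

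At b = 20% this exceeds the 8-point expected difference from step 1. In a single trial the background could therefore move the comparison either way.

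**Step 4. Whether a post-baseline restriction is enough alone.** If a fraction r of baseline abnormalities persist after dosing, the post-baseline count over all participants is br + (1 − b)p. At r = 1 this equals the step 1 rate. The restriction removes abnormalities seen only before dosing; separating new from persisting ones also requires conditioning on the baseline tracing.

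**The case against.** The strongest reply is that the SAP never says the baseline tracing is pooled into the proportions. The visit list in the lead-in describes where ECG interval data are reported; the sub-items name no visits, and the QTc-change item uses baseline only as a reference. That is fair. Counting baseline is the natural reading of an unrestricted at-least-one count under that lead-in, but it is not an explicit instruction. What stands is that nothing excludes the baseline tracing.

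Second, a reader might infer that some participants are in fact counted as events before dosing. The documents do not support that. Criterion 5 shows that it is possible, not that it occurred. It also depends on an undefined term: if abnormal ECG means clinically significant, eligible participants would have essentially no baseline events, apart from any eligibility exceptions approved under Protocol 10.1.2; if it means any deviation, they may. That choice does not settle the QTc item, which has its own numeric limit.

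Third, the fall in ratio from 3 to 1.3 looks dramatic, but it rests wholly on assumed rates, and the same inputs move the difference only from 10 to 8 points. One b is also used for both measures, although QTc above the limit and any abnormal ECG need not be equally common.

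Fourth, these summaries are descriptive. Treatment-emergent adverse events are reported too, and Protocol 13.1 counts worsening of a pre-existing condition as an adverse event, so clinically important new findings have another route. This lowers the stakes but does not make the ECG proportions interpretable.

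Finally, counting only participants normal at baseline would drop worsening in the others. That objection is correct, and it is why the shift table is needed.

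**Conclusion.** The point holds as a gap in the definition of two descriptive safety measures, and closing it is a cheap improvement. As written, SAP 5.2 allows a pre-dose-only abnormality to count as an event, in contrast to the treatment-emergent rule for adverse events and the on-treatment rule for suicidality.

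The size cannot be derived from the documents. In expectation the risk difference shrinks by (1 − b): nothing at b = 0, and one to three points out of ten for b between 10% and 30% under the assumed 15% and 5%. This requires baseline tracings to be counted and abnormal to include findings that eligibility permits.

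A reader might go further and conclude that the plan necessarily masks a drug effect, or always pulls the arms together. The documents do not support that. Attenuation holds only on average; with about 23 per arm, baseline imbalance could also produce an apparent difference or enlarge a real one. The primary efficacy analysis is unaffected.

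**What to change.** In SAP 5.2:
1. State that both proportions count post-baseline tracings only, and name the visits. Protocol 9.2.1 and 9.2.2 mention a week-12 EKG that Appendix 1 and the SAP visit list do not show, so these passages should be reconciled.
2. Report new abnormal ECG and new QTc above the SAP limit among participants normal at baseline, with the denominator shown by arm.
3. Add a table by arm of baseline status against worst post-baseline status, so that participants abnormal at baseline stay visible.
4. State whether abnormal ECG means any abnormality or a clinically significant one.

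The cost is a few lines of SAP text and one extra table from data already collected, with no new procedures. The new-abnormality count has a somewhat smaller denominator, for example 18.8 instead of 23.5 per arm at b = 20%.
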